## 12.6 Primary Analysis

The primary analysis evaluates the change from baseline in PD, which will be calculated for each patient across all sites with a baseline PD  $\geq 4$  mm, resulting in one value per patient per endpoint for each visit (baseline, Month 3 and 6).

The primary analysis will be performed on the As Exposed Set using a mixed model for repeated measurements (MMRM) for only subjects who have used cigarettes and/or Heatsticks. The model will include the PD change from baseline as the dependent variable, adjusting for daily cigarette consumption and disease severity at V1, full mouth PD at V1, exposure group and its interaction with visit. Site will be included as a random effect. The modeling assumptions will be evaluated and the model fit will be assessed by the analysis of the residual (diagnostics) and by comparing the values predicted vs. the observed values (calibration).

Additionally, the analysis will be performed on the FAS, PP and Adherent Use populations as a supportive sensitivity analysis. Additional sub group analyses such as for “Other” product use groups may be analyzed and will be defined in the SAP.

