5.2.4 Percentage for specific product consumption for dual-users

Percentage for specific product consumption (HeatSticks and cigarettes) will be defined as total consumption of the specific product divided by all product consumption (excluding all other products) from post randomization until date of last self-reported product use.

$$\left[\begin{aligned} &\text{Percentage for specific product consumption to all product consumption (\%)} \\ &= \frac{\text{Total consumption of a given product}}{\text{Total consumption of Heatsticks and cigarettes}} \end{aligned} \right]$$

5.2.5 Average cigarette consumption at V3 and V4.

For each patient regardless of randomized arm, the average daily cigarette consumption at V3 and V4 will be calculated. This will be done as described in section 5.2.2 except that total consumption up to each visit and days elapsed since randomization will be used.

$$\left[\text{Daily product consumption at } V_i = \frac{\text{Total product consumption until } V_i}{\text{Total number of days until } V_i} \right], i = 3, 4$$

where V_3 is Visit 3 and V_4 is Visit 4.

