9.1.5 Handling of Dropouts or Missing Data

9.1.5.1 Drop Out (withdrawal)

Subjects who dropped out from the study in any way will have their data analyzed up to the point of last contact.

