9.5.1.1 Primary Analyses

Primary Analysis of Change from Baseline in PD at V4	
Population	
 • As Exposed Set For this analysis, subjects categorized in IQOS user, cigarette user or dual user will be included with initial PD \geq 4mm will be included.
	The primary analysis will be performed on the As Exposed Set using a mixed model for repeated measurements (MMRM). Estimates of difference in PD will be calculated for Cigarette User against IQOS User categories and Cigarette User against Dual User categories. The model will include the PD change from baseline as the dependent variable, adjusting for the following covariates; 
 1. Daily cigarette consumption at V1 2. Disease severity at V1 3. Full mouth PD at V1 4. Visit 5. Product use pattern (IQOS user, cigarette smoker or dual user) 6. Interaction between visit and product use

Confidentiality Statement

Data and information contained in this document are considered to constitute trade secrets and confidential commercial information, and the legal protections provided to such trade secrets and confidential information are hereby claimed under the provisions of applicable law. No part of this document may be publicly disclosed without the written consent of Philip Morris Products S.A

Primary Analysis of Change from Baseline in PD at V4

7. Average daily cigarette use at each visit
8. Interaction between Daily cigarette consumption at V1 and product use
9. Interaction between Disease severity at V1 and product use
10. Time since last SRP
11. Number of target tooth/teeth extracted
12. Number of non-measured target tooth/teeth extracted
13. Baseline tooth mobility

Site will be included as a random effect. The degrees of freedom will be adjusted by using Kenward Roger (KR) method. A Toeplitz structure (“type=toep”) will be specified as the covariance matrix. However, other covariance structures may be used in case of non-convergence. Covariates 8-12 will be assessed for adequacy in the model using a step-wise (backward) approach through the following algorithm.

1. Fit a full model using maximum likelihood with all covariates
2. Perform a likelihood ratio test for the full model and drop the covariate with the largest p-value for the likelihood ratio statistic if it is more than 0.05.
3. Drop one covariate (only covariates 7-14) and re-fit the model.

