4. Perform a likelihood ratio test and drop the covariate with the largest p-value for the likelihood ratio statistic if it is more than 0.05.
5. Repeat steps 2 and 3 until no more covariates can be dropped.
6. Refit the final model with the covariates remaining in the model and estimate PD for each product use group using the restricted likelihood method.

Note that other covariates may be added if deemed necessary.

Number of subjects included in analysis, regression coefficients, 95% CI for regression coefficient, p-value for regression coefficient, Least Squares (LS) means (Cigarette User, IQOS User and Dual-User categories), Difference in LS Means (Cigarette User vs IQOS User/Dual-User) and 95% CI for Difference in LS Means will be presented.

The model fit will be assessed by the analysis of the residual (diagnostics) and by comparing the values predicted vs. the observed values (calibration).

Confidentiality Statement

Data and information contained in this document are considered to constitute trade secrets and confidential commercial information, and the legal protections provided to such trade secrets and confidential information are hereby claimed under the provisions of applicable law. No part of this document may be publicly disclosed without the written consent of Philip Morris Products S.A

Primary Analysis of Change from Baseline in PD at V4	
	The residuals, predicted vs observed values from the final model will be plotted.
Target visit	: V4 (6 Months)
Sample code	
ODS GRAPHICS ON;
 
PROC MIXED DATA = X METHOD=ML (REML for final model);
 
CLASS Product_use Subject Visit site;
 
MODEL PD reduction (Dependent variable) = avisit avisit*trt01a 3 4 5 6 7 8 9 10 11 12/ ddfm=kr outp=dsn residuals vciry;
 
RANDOM Site;
 
REPEATED / subject=visit (subject) type=toep;
 
LSMEANS Product_use * Visit / CL ALPHA=0.025 DIFF E UPPER;
 
RUN;
 
Where 1 2 3 4 5 6 7 8 9 10 11 12 refers to the covariates.
 
ODS GRAPHICS OFF;

Output	
15.4.5.1 Primary Analysis of Change from Baseline in Pocket Depth (mm) at V4 with Initial Pocket Depth \geq 4 mm - As Exposed Set -
 
15.4.5.2 Regression Coefficients and Graphical Diagnostics of Primary Analysis of Change from Baseline in Pocket Depth (mm) at V4 - As Exposed Set -
 
15.4.5.3 Primary Analysis of Change from Baseline in Pocket Depth (mm) at V4: Variables Dropped - As Exposed Set -

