9.5.2 Secondary Analyses

9.5.2.1 Secondary Analysis

Analysis of Change from Baseline in PD at V3 and CAL at V4 / V3	
Population	: • As Exposed Set
Contents	: The model will include the PD (or CAL) change from baseline as the dependent variable, adjusting for the following covariates; 
 • The statistical model is described in section 9.5.1. Note that “Full mouth PD at V1” will be replaced as “Full mouth CAL at V1”
Target visit	: • V3 (3 Months) for PD • V3 (3 Months) and V4 (6 Months) for CAL
Remarks	: • Statistical tests for PD at V3, CAL and V4 and V3 are performed in a sequential manner as detailed in section 9.1.8. • The same model for the primary analysis will be used with both V3 and V4 data included; PD at 3 months will be reported only if the test for PD between Cigarette User and IQOS User categories at 6 months is significant. • If the test between Cigarette User and IQOS Users Categories for PD is significant at V3, then the model with change from baseline CAL will be fitted with both V3 and V4 data and the test between CC and IQOS for CAL at V4 will be reported. • If the test between Cigarette User and IQOS User categories for CAL at V4 is significant, then the test between Cigarette User and IQOS User Categories for CAL at V3 will be reported.
Sample code	Refer to “ Primary Analysis ”
Output	15.4.7.1 Analysis of Change from Baseline in Pocket Depth (mm) at V3 with Initial Pocket Depth \geq 4 mm - As Exposed Set - 15.4.7.2 Regression Coefficients and Graphical Diagnostics of Analysis of Change from Baseline in Pocket Depth (mm) at V3- As Exposed Set - 15.4.7.3 Analysis of Change from Baseline in Clinical Attachment Level (mm) with Initial Pocket Depth \geq 4 mm - As Exposed Set -

Confidentiality Statement

Data and information contained in this document are considered to constitute trade secrets and confidential commercial information, and the legal protections provided to such trade secrets and confidential information are hereby claimed under the provisions of applicable law. No part of this document may be publicly disclosed without the written consent of Philip Morris Products S.A

Analysis of Change from Baseline in PD at V3 and CAL at V4 / V3

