Analysis Variables	: 
 • NEQ adjusted for creatinine • Total NNAL adjusted for creatinine • CEMA adjusted for creatinine
Target visit	: 
 • Baseline • V3 (3 months) • V4 (6 months)
Remarks	: 
 • Statistical tests for each BoExp at V3 and V4 performed in a sequential manner as detailed in section 9.1.8. • The same model for the analysis will be used with both V3 and V4 data included, if the test between CC and IQOS is significant at V4 then the test between CC and IQOS for V3 will be reported in the same table.
Sample code	Refer to " Primary Analysis "
Output	
15.4.7.5 Analysis of Relative Change from Baseline in NEQ (mg/g) (Biomarkers of Exposure) (Geometric LS means, Ratio of Geometric Means and p-value) - As Exposed Set -
 
15.4.7.6 Regression Coefficients and Graphical Diagnostics of Analysis of Relative Change from Baseline in NEQ (mg/g) (BoExp) Geometric Mean Value - As Exposed Set -
 
15.4.7.7 Analysis of Relative Change from Baseline in Total NNAL (pg/mL) (Biomarkers of Exposure) (Geometric LS means, Ratio of Geometric Means and p-value) - As Exposed Set -
 
15.4.7.8 Regression Coefficients and Graphical Diagnostics of Analysis of Relative Change from Baseline in Total NNAL (pg/mL) (Biomarkers of Exposure) Geometric Mean Value - As Exposed Set -

Confidentiality Statement

Data and information contained in this document are considered to constitute trade secrets and confidential commercial information, and the legal protections provided to such trade secrets and confidential information are hereby claimed under the provisions of applicable law. No part of this document may be publicly disclosed without the written consent of Philip Morris Products S.A

Summary Table of Analysis for BoExp Geometric mean value

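### The SAP's sample code makes each visit its own block, so the primary MMRM would treat a patient's Month 3 and Month 6 values as independent

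*SAP*

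**What the plan says.** SAP 9.5.1.1 states: "The primary analysis will be performed on the As Exposed Set using a mixed model for repeated measurements (MMRM"). It adds Kenward-Roger degrees of freedom, site as a random effect, and a Toeplitz structure, which "will be specified as the covariance matrix. However, other covariance structures may be used in case of non-convergence". The sample code beneath it contains "REPEATED / subject=visit (subject) type=toep" and a RANDOM statement for site only. There is no patient random effect.

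Protocol 12.6 describes the outcome as a change calculated over each patient's qualifying sites, "resulting in one value per patient per endpoint for each visit (baseline, Month 3 and 6"). For Month 3 PD and for clinical attachment level (CAL), SAP 9.5.2.1 says: "The same model for the primary analysis will be used with both V3 and V4 data included". The biomarker (BoExp) analysis says: "The same model for the analysis will be used with both V3 and V4 data included". These analyses, and the supportive ones in 9.5.1.2 and 9.5.2.2, give no code of their own and refer back to the primary analysis.

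On missing data, SAP 9.1.5.1 says: "Subjects who dropped out from the study in any way will have their data analyzed up to the point of last contact". No imputation of outcomes is planned.

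**The concern.** In `PROC MIXED` the `subject=` effect on the REPEATED statement defines the blocks within which residuals may correlate. Naming visit nested in patient puts a patient's two visits in different blocks. The analysis is then a repeated-measures model in name only.

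Three consequences follow if the line is run as written:

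- **(a) Missing Month 6 data.** A patient seen at V3 but not V4 can correct the V4 estimate essentially only through the V3–V4 correlation. With that correlation fixed at zero, the protection against dropout that depends on V3 response is lost.
- **(b) Covariate selection.** The likelihood-ratio tests used for backward deletion count two visits as two patients, so for patient-level covariates they are too liberal.
- **(c) The primary test with covariate 7.** Covariate 7 is average daily cigarette use at each visit. SAP 5.2.5 derives it like overall daily use, "except that total consumption up to each visit and days elapsed since randomization will be used". It nearly separates the product groups, so the adjusted contrast leans on a between-patient slope whose standard error is understated.

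The code also departs from the text elsewhere. The MODEL line carries covariates 3 to 12, while the text lists 13. Covariates 1 and 2 are the stratification factors. The code sets ALPHA to 0.025, although SAP 9.1.8 and 9.5.1.1 call for 95% intervals, two-sided under 9.1.8.

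**Working it through.** **The plan's own figure.** Inputs from Protocol 12.2: one-sided alpha 2.5%, power 80%, SD 0.5 mm, difference 0.25 mm. The normal formula gives n = 2(1.960 + 0.842)² × 0.5² / 0.25² = 62.8 per group. The t-based version gives 64 (power 80.1%). Then 64 / (1 − 0.25) = 85.3, rounded up to 86 per arm and 172 in total. This reproduces the plan. It comes from a two-sample comparison and does not depend on the REPEATED statement.

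**Block structure.** With 172 patients and two post-baseline visits:

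| | Blocks | Block size | Residual parameters |
|---|---|---|---|
| As coded, visit(subject) | 344 | 1 | variance only |
| As the text implies, subject | 172 | 2 | variance and V3–V4 covariance |

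A 1×1 Toeplitz matrix is a single variance. The site effect adds only a covariance common to everyone at a site. Switching structure on non-convergence would not change the block definition.

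The documents give no V3–V4 correlation ρ, so it is varied below. The SD is 0.5 mm throughout.

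**(a) Dropout depending on V3.** With equal visit variances, bias in a group's V4 mean = ρ × (shift in V3 mean among completers). Assume 15% dropout (SAP 6), all after V3, on a logistic scale.

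- Odds tripling per SD of V3 response: the completers' V3 mean shifts by 0.142 SD = 0.071 mm. Selection in one group only gives 0.3 × 0.071 = 0.02 mm to 0.8 × 0.071 = 0.06 mm. Opposite directions in the two groups double this, to 0.04–0.11 mm.
- Odds doubling: shift 0.098 SD = 0.049 mm, giving 0.015–0.04 mm and 0.03–0.08 mm.
- The same selection in both groups gives a bias of about 0.

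Simulation with 86 per arm (4,000 trials per scenario) gives the same ranges, and a bias of 0.00 when the patient-level correlation is used.

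A separate simulation used steeper one-arm selection (odds multiplied by about 4 per SD, roughly 16% dropout in that arm). One-sided error was 5.7%, 7.3%, 11.8% and 15.2% at ρ = 0.3, 0.5, 0.7 and 0.9, against 2.0–2.6% with a patient block. Under purely random 15% dropout it was 2.6–3.5% against 2.1–3.1%.

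**(b) Selection at 0.05.** For a covariate that is constant within patient, the true variance of its coefficient is (1 + ρ) times the one the coded model assumes. The false-retention rate is then P(χ²₁ > 3.841 / (1 + ρ)). The simulation used 2,000 null trials with 64 per group:

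| ρ | Formula | Simulated, as coded | Simulated, patient block |
|---|---|---|---|
| 0.3 | 8.6% | 9–10% | 5–6% |
| 0.5 | 11.0% | 11–12% | 5–6% |
| 0.65 | 12.7% | 14% | 5–6% |
| 0.8 | 14.4% | 15–17% | 5–6% |

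**(c) One-sided Month 6 error with covariate 7.** If the adjusted contrast were driven wholly by the cigarette slope, and cigarette use were constant within patient, the error would be 1 − Φ(1.960 / √(1 + ρ)). This is 4.3%, 5.5% and 7.2% at ρ = 0.3, 0.5 and 0.8. The simulation assumed cigarette users at a mean of 16 per day (SD 4, 6 or 8), IQOS users at 0.5 or 1, a V3–V4 correlation of use of 0.8–0.95, and 64 per group. Its results fall below those limits:

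| | As coded | Patient block |
|---|---|---|
| With covariate 7, ρ = 0.3 | 3.1–4.1% | 2.5–2.7% |
| With covariate 7, ρ = 0.5–0.8 | 3.7–6.6% | 1.8–3.0% |
| Without covariate 7 | 1.9–2.4% | 1.9–2.4% |

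Monte Carlo error is about 0.3–0.5 points for (c) and 0.5–0.8 points for (b). Simulations (b) and (c) use complete data and equal variances, and omit the site effect and dual users.

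**The case against.** The strongest reply is that the governing text is right and the block is labelled sample code. It has numerals in place of covariates, and variable names in MODEL that differ from those in CLASS. A programmer must rewrite it and may correct the REPEATED line while doing so. That is fair, and it is why every consequence above is conditional. But the line contains no placeholder that would prompt a correction, and it is the only executable specification for this and the dependent analyses.

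Several objections on size also stand in part:

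- The 15% is total dropout. If only half leaves after V3, the bias under tripled odds falls to 0.01–0.03 mm (one group) or 0.02–0.06 mm (opposite directions).
- The documents describe no dropout mechanism that differs by group. The zero bias with a patient block holds because the simulated dropout depends only on V3.
- In (b), only the two baseline-by-product interactions (covariates 8 and 9) are clearly constant within patient.
- In (c), comparing groups at a common cigarette use that they hardly share is a separate problem, which correcting the block does not cure. The effect in (c) also disappears if covariate 7 is dropped. The text is unclear on whether it may be, giving the removable set once as 8–12 and once as 7–14.
- On the MODEL line, the legend under the code names covariates 1 to 12. The absence of 1 and 2 may therefore be a slip, with visit and its product interaction sitting in their slots. Covariate 13 is in neither.

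None of this alters the block structure.

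**Conclusion.** The concern holds. As written, the code contradicts the SAP's own method: with one record per patient per visit it fits independent residuals and leaves the patient-level V3–V4 correlation unmodelled.

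The harm depends on conditions the documents do not settle. It is small with complete data or random dropout when covariate 7 is absent. It matters if dropout depends on V3 response differently by group, if the likelihood-ratio selection is run, or if covariate 7 stays in the model. The size of each effect also depends on ρ, which is unknown. The sample size is unaffected. This should be corrected before the analysis is programmed; it is not a flaw in the design.

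**What to change.** Replace the statement with `REPEATED visit / subject=subject type=toep`. An unstructured matrix (`type=un`) is a reasonable alternative: with two visits it needs only three parameters and allows unequal visit variances. It would, however, require amending the text, which names Toeplitz.

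In the same edit:

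- use one visit variable and one product variable throughout CLASS, MODEL, REPEATED and LSMEANS;
- put covariates 1, 2 and 13 in the MODEL line, and make the legend agree with the list in the text;
- state one removable set for the backward selection;
- print two-sided 95% limits beside the one-sided p-value.

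The cost is a few corrected lines in the SAP. Data collection, sample size and the stated method are unchanged.

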9.5.1.2 Supportive Analysis for Primary Objective

Supportive/Sensitivity Analyses of Change from Baseline in PD	
Population	: 
 Full Analysis Set Per Protocol Set
Contents	: Refer to " Primary Analysis "
Target visit	: 
 V3 (3 months) V4 (6 months)

Confidentiality Statement

Data and information contained in this document are considered to constitute trade secrets and confidential commercial information, and the legal protections provided to such trade secrets and confidential information are hereby claimed under the provisions of applicable law. No part of this document may be publicly disclosed without the written consent of Philip Morris Products S.A

Supportive/Sensitivity Analyses of Change from Baseline in PD	
Sample code	Refer to " Primary Analysis "
Output	
15.4.6.1 Analysis of Change from Baseline in Pocket Depth (mm) with Initial Pocket Depth \geq 4 mm - Full Analysis Set, Per Protocol Set -
 
15.4.6.2 Regression Coefficients and Graphical Diagnostics of Analysis of Change from Baseline in Pocket Depth (mm) - Full Analysis Set , Per Protocol Set -

Summary Table of Mean Full-Mouth PD by (i) Daily Cigarette Consumption, (ii) Disease Severity (iii) Age group	
Population	: 
 As Exposed Set Full Analysis Set Per Protocol Set
Contents	: Refer to Descriptive statistics
Analysis variables	: 
 Mean full-mouth PD Change of mean full-mouth PD
Target visit	
 Baseline V3 (3 months) V4 (6 months)
Remarks	Output titles to be changed depending on target population.
Output	
15.2.6.1 Summary Table of Mean Full-Mouth Pocket Depth (mm) by Disease Severity - As Exposed Set, Full Analysis Set, Per Protocol Set -
 
15.2.6.2 Summary Table of Mean Full-Mouth Pocket Depth (mm) by Daily Cigarette Consumption - As Exposed Set, Full Analysis Set, Per Protocol Set -
 
15.2.6.3 Summary Table of Mean Full-Mouth Pocket Depth (mm) by Sex - As Exposed Se, Full Analysis Set, Per Protocol Set -
 
15.2.6.4 Summary Table of Mean Full-Mouth Pocket Depth (mm) by Age Group - As Exposed Set, Full Analysis Set, Per Protocol Set -

Confidentiality Statement

9.5.2 Secondary Analyses

9.5.2.1 Secondary Analysis

Analysis of Change from Baseline in PD at V3 and CAL at V4 / V3	
Population	: • As Exposed Set
Contents	: The model will include the PD (or CAL) change from baseline as the dependent variable, adjusting for the following covariates; 
 • The statistical model is described in section 9.5.1. Note that “Full mouth PD at V1” will be replaced as “Full mouth CAL at V1”
Target visit	: • V3 (3 Months) for PD • V3 (3 Months) and V4 (6 Months) for CAL
Remarks	: • Statistical tests for PD at V3, CAL and V4 and V3 are performed in a sequential manner as detailed in section 9.1.8. • The same model for the primary analysis will be used with both V3 and V4 data included; PD at 3 months will be reported only if the test for PD between Cigarette User and IQOS User categories at 6 months is significant. • If the test between Cigarette User and IQOS Users Categories for PD is significant at V3, then the model with change from baseline CAL will be fitted with both V3 and V4 data and the test between CC and IQOS for CAL at V4 will be reported. • If the test between Cigarette User and IQOS User categories for CAL at V4 is significant, then the test between Cigarette User and IQOS User Categories for CAL at V3 will be reported.
Sample code	Refer to “ Primary Analysis ”
Output	15.4.7.1 Analysis of Change from Baseline in Pocket Depth (mm) at V3 with Initial Pocket Depth \geq 4 mm - As Exposed Set - 15.4.7.2 Regression Coefficients and Graphical Diagnostics of Analysis of Change from Baseline in Pocket Depth (mm) at V3- As Exposed Set - 15.4.7.3 Analysis of Change from Baseline in Clinical Attachment Level (mm) with Initial Pocket Depth \geq 4 mm - As Exposed Set -

Confidentiality Statement

Data and information contained in this document are considered to constitute trade secrets and confidential commercial information, and the legal protections provided to such trade secrets and confidential information are hereby claimed under the provisions of applicable law. No part of this document may be publicly disclosed without the written consent of Philip Morris Products S.A

Analysis of Change from Baseline in PD at V3 and CAL at V4 / V3

	
15.4.7.4 Regression Coefficients and Graphical Diagnostics of Analysis of Change from Baseline in Clinical Attachment Level (mm) - As Exposed Set -
 
15.4.7.17 Analysis of Change from Baseline in Pocket Depth (mm) at V3: Variables Dropped - As Exposed Set -
 
15.4.7.18 Analysis of Change from Baseline in Clinical Attachment Level (mm): Variables Dropped - As Exposed Set -

--	---

Summary Table of Analysis for BoExp Geometric mean value

Population	:	
 As Exposed Set
Contents	:	
The analysis will be performed on the As Exposed Set using a mixed model for repeated measurements (MMRM).
 
The model will include the change from baseline of log transformed BoExp adjusted for creatinine as the dependent variable, adjusting for the following covariates;
 
 Daily cigarette consumption Sex Visit Baseline level of BoExp Product use Interaction between visit and product use Interaction between Daily cigarette consumption at V1 and product use Average daily cigarette use at each visit 
Site will be included as a random effect.
 
For analysis, PROC MIXED will be used. Site will be included as RANDOM effect.
 
Degree of freedom will be adjusted by using KR.
 
Number of patients included in analysis, regression coefficient, 95% CI for regression coefficient, p-value for regression coefficient,

Confidentiality Statement

Data and information contained in this document are considered to constitute trade secrets and confidential commercial information, and the legal protections provided to such trade secrets and confidential information are hereby claimed under the provisions of applicable law. No part of this document may be publicly disclosed without the written consent of Philip Morris Products S.A

Summary Table of Analysis for BoExp Geometric mean value	
	
Geometric LS means (IQOS-cigarette), Ratio of Geometric LS Means and 95% CI for Ratio of Geometric LS means at 3 and 6 month for each product use will be presented.
 
The modelling assumptions will be evaluated and the model fit will be assessed by the analysis of the residual (diagnostics) and by comparing the values predicted vs. the observed values (calibration).
 
 • Predicted value and observed value will be plotted.
Analysis Variables	: 
 • NEQ adjusted for creatinine • Total NNAL adjusted for creatinine • CEMA adjusted for creatinine
Target visit	: 
 • Baseline • V3 (3 months) • V4 (6 months)
Remarks	: 
 • Statistical tests for each BoExp at V3 and V4 performed in a sequential manner as detailed in section 9.1.8. • The same model for the analysis will be used with both V3 and V4 data included, if the test between CC and IQOS is significant at V4 then the test between CC and IQOS for V3 will be reported in the same table.
Sample code	Refer to " Primary Analysis "
Output	
15.4.7.5 Analysis of Relative Change from Baseline in NEQ (mg/g) (Biomarkers of Exposure) (Geometric LS means, Ratio of Geometric Means and p-value) - As Exposed Set -
 
15.4.7.6 Regression Coefficients and Graphical Diagnostics of Analysis of Relative Change from Baseline in NEQ (mg/g) (BoExp) Geometric Mean Value - As Exposed Set -
 
15.4.7.7 Analysis of Relative Change from Baseline in Total NNAL (pg/mL) (Biomarkers of Exposure) (Geometric LS means, Ratio of Geometric Means and p-value) - As Exposed Set -
 
15.4.7.8 Regression Coefficients and Graphical Diagnostics of Analysis of Relative Change from Baseline in Total NNAL (pg/mL) (Biomarkers of Exposure) Geometric Mean Value - As Exposed Set -

Confidentiality Statement

Data and information contained in this document are considered to constitute trade secrets and confidential commercial information, and the legal protections provided to such trade secrets and confidential information are hereby claimed under the provisions of applicable law. No part of this document may be publicly disclosed without the written consent of Philip Morris Products S.A

Summary Table of Analysis for BoExp Geometric mean value

	
15.4.7.9 Analysis of CEMA (ng/mL) (Biomarkers of Exposure) Geometric Mean Value - As Exposed Set -
 
15.4.7.10 Regression Coefficients and Graphical Diagnostics of Analysis of Relative Change from Baseline in CEMA (ng/mL) (Biomarkers of Exposure) - As Exposed Set -
 
15.4.7.11 Analysis of NEQ Adjusted for Creatinine (mg/dL) (Biomarkers of Exposure) Geometric Mean Value - As Exposed Set -
 
15.4.7.12 Regression Coefficients and Graphical Diagnostics of Analysis of Relative Change from Baseline in NEQ Adjusted for Creatinine (mg/g creat) (Biomarkers of Exposure) - As Exposed Set -
 
15.4.7.13 Analysis of Total NNAL Adjusted for Creatinine (pg/mL creat) (Biomarkers of Exposure) Geometric Mean Value - As Exposed Set -
 
15.4.7.14 Regression Coefficients and Graphical Diagnostics of Analysis of Change from Baseline in Total NNAL Adjusted for Creatinine (pg/mL creat) (Biomarkers of Exposure) - As Exposed Set -
 
-
 
15.4.7.15 Analysis of CEMA Adjusted for Creatinine (ng/mL creat) (Biomarkers of Exposure) Geometric Mean Value - As Exposed Set -
 
15.4.7.16 Regression Coefficients and Graphical Diagnostics of Analysis of Change from Baseline in CEMA Adjusted for Creatinine (ng/mL creat) (Biomarkers of Exposure) - As Exposed Set -

--	--

Summary Table of Mean Full-Mouth CAL

Population	:	
 • As Exposed Set ➤ Product use pattern categories
Contents	:	Refer to Descriptive statistics
Analysis variables	:	
 • Mean full-mouth CAL • Change of mean full-mouth CAL

Confidentiality Statement

Data and information contained in this document are considered to constitute trade secrets and confidential commercial information, and the legal protections provided to such trade secrets and confidential information are hereby claimed under the provisions of applicable law. No part of this document may be publicly disclosed without the written consent of Philip Morris Products S.A

Summary Table of Mean Full-Mouth CAL	
Target visit	
 • Baseline • V3 (3 months) • V4 (6 months)
Output	
15.1.7.5 Plot of Full-Mouth Clinical Attachment Level (mm) and 95% CI vs Visit by Product Use Categories - As Exposed Set -
 
15.1.7.6 Plot of Full-Mouth Clinical Attachment Level (mm) and 95% CI vs Visit by Product Use Categories and Disease Severity - As Exposed Set -
 
15.1.7.7 Plot of Full-Mouth Clinical Attachment Level (mm) and 95% CI vs Visit by Product Use Categories and Daily Cigarette Consumption - As Exposed Set -
 
15.1.7.8 Plot of Full-Mouth Clinical Attachment Level (mm) and 95% CI vs Visit by Product Use Categories, Disease Severity and daily Cigarette Consumption - As Exposed Set -
 
15.1.7.9 Plot of Full-Mouth Clinical Attachment Level (mm) and 95% CI vs Visit in Patients with Initial Pocket Depth ≥ 4 mm - As Exposed Set -
 
15.2.7.1 Descriptive Statistics of Mean Full-Mouth Clinical Attachment Level (mm) and 95% CI- As Exposed Set -
 
15.3.7.1 Listing for Clinical Attachment Level (mm) Value - As Exposed Set -
 
15.1.9.5 Plot of Clinical Attachment Loss (mm) for initials sites with Pocket Depth ≥ 4 mm - As Exposed Set -

Summary Table of Change in PD in Sites Based on Baseline PD Level	
Population	: • As Exposed Set
Contents	: Refer to Descriptive statistics In addition, a bar graph representing the mean PD in sites with different Initial PD, and a heatmap of PD against time by product use category will be created.
Analysis variables	: • PD • Change of mean PD

Confidentiality Statement

Data and information contained in this document are considered to constitute trade secrets and confidential commercial information, and the legal protections provided to such trade secrets and confidential information are hereby claimed under the provisions of applicable law. No part of this document may be publicly disclosed without the written consent of Philip Morris Products S.A

Summary Table of Change in PD in Sites Based on Baseline PD Level	
Category	Initial PD of 
 • PD < 4 mm • 4 mm ≤ PD < 5mm • 5 mm ≤ PD < 6 mm • 6 mm ≤ PD < 7 mm • PD ≥ 7 mm
Target visit	
 • Baseline • V3 (3 months) • V4 (6 months)
Output	15.2.7.2 Summary Table of Change in Pocket Depth (mm) in Sites based on Initial Pocket Depth (mm) Level - As Exposed Set - 15.1.7.14 Mean Pocket Depth (mm) in Sites with Different Initial Pocket Depth (mm) - As Exposed Set - 15.1.9.3 Heatmap of Pocket Depth (mm) Level Count by Time and Product Use Categories - As Exposed Set -

Summary Table of Change in CAL in Sites Based on Baseline PD Level	
Population	: • As Exposed Set
Contents	: Refer to Descriptive statistics
Analysis variables	: 
 • CAL • Change of mean CAL
Category	Initial PD of 
 • PD < 4 mm • 4 mm to ≤ PD < 5mm • 5 mm to ≤ PD < 6 mm • 6 mm to ≤ PD < 7 mm • PD ≥ 7 mm
Target visit	
 • Baseline • V3 (3 months)

Confidentiality Statement

Data and information contained in this document are considered to constitute trade secrets and confidential commercial information, and the legal protections provided to such trade secrets and confidential information are hereby claimed under the provisions of applicable law. No part of this document may be publicly disclosed without the written consent of Philip Morris Products S.A

Summary Table of Change in CAL in Sites Based on Baseline PD Level	
	
 V4 (6 months)
Output	15.2.7.3 Summary Table of Change in Clinical Attachment Level (mm) in Sites based on Initial Pocket Depth Level (mm) - As Exposed Set -

Shift Table of Change in Number of Sites with PD Level	
Population	: 
As Exposed Set
Contents	: Provide shift table with percentage based on PD level by product use pattern
Category	PD level at baseline 
 < 4 mm 4 mm ≤ PD < 5mm 5 mm ≤ PD < 6 mm 6 mm ≤ PD < 7 mm PD ≥ 7 mm
Target visit	
 V3 (3 months) V4 (6 months)
Output	15.2.7.4 Shift Table in Number of Sites with Pocket Depth Level (mm) - As Exposed Set -

Summary Table of BoExp Parameters	
Population	: 
As Exposed Set➤ Product use pattern categories
Contents	: In addition to the contents defined in “ Descriptive statistics ”, the number of values below LLOQ or above ULOQ will be presented in each summary table. If more than 50% of the data are below LLOQ, only the number and percentage of values below LLOQ will be reported in the summary together with the minimum and maximum values. In addition, the geometric means, CV and geometric relative change will be presented.

Confidentiality Statement

Data and information contained in this document are considered to constitute trade secrets and confidential commercial information, and the legal protections provided to such trade secrets and confidential information are hereby claimed under the provisions of applicable law. No part of this document may be publicly disclosed without the written consent of Philip Morris Products S.A

Summary Table of BoExp Parameters	
	Figures of NEQ, total NNAL, CEMA against product use category will be plotted. In addition, scatter plot of CEMA against time and a box plot of CEMA against time by product use will also be prepared.
Analysis variables	: 
 • NEQ adjusted for creatinine • Total NNAL adjusted for creatinine • CEMA adjusted for creatinine
Target visit	
 • Baseline • V3 (3 months) • V4 (6 months)
Output	
15.2.7.5 Summary Table of Biomarkers of Exposure Parameters (NEQ (mg/g)) - As Exposed Set -
 
15.2.7.6 Summary Table of Biomarkers of Exposure Parameters (Total NNAL (pg/mL)) - As Exposed Set -
 
15.2.7.7 Summary Table of Biomarkers of Exposure Parameters (CEMA (ng/mL)) - As Exposed Set -
 
15.2.7.8 Summary Table of Biomarkers of Exposure Parameters (NEQ adjusted for creatinine (mg/g creat)) - As Exposed Set -
 
15.2.7.9 Summary Table of Biomarkers of Exposure Parameters (Total NNAL adjusted for creatinine (pg/mg creat)) - As Exposed Set -
 
-
 
15.2.7.10 Summary Table of Biomarkers of Exposure Parameters (CEMA adjusted for creatinine (ng/mg creat)) - As Exposed Set -
 
15.3.7.2 Listing for Biomarkers of Exposure - As Exposed Set -
 
15.1.4.1 Plot of NEQ adjusted for creatinine (mg/g creat) vs Visit by Product Use Categories - As Exposed Set -
 
15.1.4.2 Plot of Total NNAL adjusted for creatinine (pg/mg creat) vs Visit by Product Use Categories - As Exposed Set -
 
15.1.4.3 Plot of CEMA adjusted for creatinine (ng/mg creat) vs Visit by Product Use Categories - As Exposed Set -
 
15.1.7.15 Scatter Plot of CEMA adjusted for creatinine (ng/mg creat) vs Time - As Exposed Set -
 
15.1.7.16 Box Plot of CEMA adjusted for creatinine (ng/mg creat) vs Time by Product Use Categories - As Exposed Set -

Confidentiality Statement

Data and information contained in this document are considered to constitute trade secrets and confidential commercial information, and the legal protections provided to such trade secrets and confidential information are hereby claimed under the provisions of applicable law. No part of this document may be publicly disclosed without the written consent of Philip Morris Products S.A

Summary Table of Periodontal Examination (BOP, GI, Tooth mobility and PCR)	
Population	: 
 • As Exposed Set 
 ➤ Product use pattern categories
Contents	: Refer to Descriptive statistics For GI and Tooth Mobility, in addition to the descriptive statistics shift tables will be constructed based on the individual (discrete) values. Scatter plots of GI and Tooth Mobility vs Visit by Product Use, Initial PD level will be plotted as well.
Analysis variables	: 
 • BOP (%) • GI • Tooth Mobility • PCR (%)
Target visit	
 • Baseline • V3 (3 months) • V4 (6 months)
Output	
15.2.7.11 Descriptive Statistics of Periodontal Examination (Bleeding On Probing (%)) - As Exposed Set -
 
15.2.7.12 Descriptive Statistics of Periodontal Examination (Gingival Index) - As Exposed Set -
 
15.2.7.13 Descriptive Statistics of Periodontal Examination (Tooth Mobility) - As Exposed Set -
 
15.2.7.14 Descriptive Statistics of Periodontal Examination (Plaque Control Record (%)) - As Exposed Set -
 
15.2.7.15 Shift Table in Number of Each Category for Gingival Index - As Exposed Set -
 
15.2.7.16 Shift Table in Number of Each Category for Tooth Mobility - As Exposed Set -
 
15.3.7.3 Listing for Bleeding On Probing (%) Assessment - As Exposed Set -
 
15.3.7.4 Listing for Plaque Control Record (%) Assessment - As Exposed Set -
 
15.3.7.5 Listing for Gingival Index Assessment - As Exposed Set -
 
15.3.7.6 Listing for Calculated Bleeding On probing (%) and Plaque Control Record (%) - As Exposed Set -

Confidentiality Statement

Data and information contained in this document are considered to constitute trade secrets and confidential commercial information, and the legal protections provided to such trade secrets and confidential information are hereby claimed under the provisions of applicable law. No part of this document may be publicly disclosed without the written consent of Philip Morris Products S.A

